**Table 1 Schedule of Assessments**

Assessments	Arrival at the site	Baseline	0 Hr	1 Hr	2 Hrs	Time of Discharge	24 Hr Follow Up	Up To 28 days post 24 Hr FU
Informed consent	X							
Inclusion/exclusion criteria	X							
Demographics	X							
Medical and Surgical History	X							
Vital signs	X	X		X	X	X		
Physical examination	X							
Study Medication Administration			X					
Extent of urticaria/erythema) 		X		X	X	X		
Pruritus Severity Score 		X		X	X	X		
Sedation Score 		X		X	X	X		
Time of Discharge						X		
Concomitant medication	X	X		X	X	X	X	
Adverse events	X	X		X	X	X	X	
Follow-up Q&A Sheet							X	
Record subject self-reported AEs								X

#### 4. SEQUENCE OF PLANNED ANALYSES

All analyses outlined in this document will be carried out after:

- The study database has been authorized by the Sponsor Clinical team as complete and final.
- Protocol deviations have been identified.
- The study is officially unblinded to treatment assignments

---

## 5. DEFINING NON-INFERIORITY MARGIN

The effect of diphenhydramine injection based on patient recorded pruritus scores in comparison to placebo is unknown. Given the length of time (usually several hours) subjects indicated that urticaria started prior to ED/clinic admission or started while in ED for other diseases, it is reasonable to assume that if left untreated, there would be no spontaneous resolution within 2 hours of ED/clinic admission.

CCI

CCI

CCI

## 6. SAMPLE SIZE CONSIDERATIONS

Assuming the diphenhydramine treated group respond similar to ETtau-02 results, the common standard deviation is expected to be around CCI. A sample size of CCI subjects per arm (total CCI) is needed to provide 90% statistical power to determine that Cetirizine will be non-inferior to diphenhydramine. The sample size was calculated based on the CCI as the non-inferiority limit of the difference, using 1-sided test at alpha CCI. Sample size estimation was performed using CCI two-group t-test of equivalence in means (MTE0-1).

## 7. ANALYSIS POPULATIONS

The disposition of all subjects, including those who discontinued, will be summarized by group, using counts and frequencies in each population. Subjects will be categorized into the following analysis populations:

**Intent-To-Treat (ITT) Population:** Includes any subject who was randomized and given a Subject ID Number with intent to treat with one of the blinded study drugs. All efficacy and non-inferiority analyses will be performed on the ITT population with subjects grouped by the treatment they were randomized to receive.

---

**Safety Population (SAF):** Includes any subjects in the ITT population who actually receives a blinded study drug, regardless whether or not they complete all assessments, withdraw or are discontinued by the investigator. All safety summaries will be performed on the SAF population with subjects grouped by the treatment they actually received.

**Per Protocol Population (PP):** Includes subjects in the SAF population who complete all necessary assessments without any incidence that would potentially affect the ability to objectively assess treatment response (e.g. discontinuation, protocol deviation, use of rescue medication, etc.).

## 8. INTERIM ANALYSES

No interim analyses are planned for this study.

## 9. GENERAL CONSIDERATIONS FOR DATA ANALYSES

All statistical analyses and summaries will be performed using SAS for PC, version 9.4 ([SAS Institute](#), Cary, NC). Continuous and quantitative, variable summaries will include the number of patients (N) assessed (with non-missing values/valid cases), mean, standard deviation, minimum.

Categorical and qualitative variable summaries will include the frequency and percentage of subjects who are in the particular category. The denominator for each percentage will be the number of subjects within the population of the treatment arm (unless otherwise specified).

The assumed overall type I error rate/significance level for the primary efficacy outcome is 5%, two-sided, unless otherwise specified. Two-sided confidence limits will be evaluated at 95%, p-values from inferential tests comparing specific cohorts or subgroups will be compared to 5%.

### 9.1. Imputed and Missing Data

The primary efficacy analysis will be performed on the ITT population. Subjects may be discharged at any time after 1 hr post-treatment assessment, which would result in missing data at the 2 hr post-treatment assessment time. Therefore, assessments of pruritus, extent of urticaria, and sedation for subjects discharged prior to the 2 hr assessment will be carried forward from the last recorded score to 2 hrs and beyond.

In addition, subjects may receive rescue medication at any time post-study drug and prior to Readiness for Discharge if the attending physician deems it necessary. Any assessment of pruritus, extent of urticaria and sedation after administering rescue medication will be confounded with the response to rescue medication. If a subject is given one or more rescue medications prior to the 2 hr assessment, the last pre-rescue assessments will be carried forward to the 2 hr assessment and to any post-rescue assessments.

Since the use of rescue would always occur prior to readiness for discharge, the use of rescue will always supersede early discharge with regards to carrying the last observation forward. As long as rescue drug

---

is used, the pre-rescue score will be carried forward to all subsequent assessment including the 1hr, 2hr, and readiness-for-discharge-assessment.

Examples:

- i) If the earliest rescue is used at 30 minutes after study drug, and the patient's readiness-for-discharge is at 1.5hr, the baseline scores (the last pre-rescue score) will be carried forward to the 1hr, 2hr and discharge assessments, regardless of the existing assessments at 1hr and 1.5hr (the discharge assessment).
- ii) If the earliest rescue is used at 30 minutes after study drug, and the patient is ready for discharge at 2.5hr post study drug, the baseline scores (the last pre-rescue-score) will be carried forward to the 1hr, 2hr and discharge assessments, regardless of the existing assessments at 1hr, 2hr and 2.5hr (the discharge assessment).
- iii) If the earliest rescue is used at 3hrs after study drug, and the patient's readiness-for-discharge is at 4hrs, the 2hr scores (the last pre-rescue-scores) will be carried forward to the discharge assessment regardless the existing 4hr assessment (the discharge assessment).
- iv) For a patient without rescue drug, if readiness-for-discharge occurs at 1.5hr, the discharge assessment (1.5hr, the last obtained score) will be carried forward to 2hr.
- v) For a patient without rescue drug, if readiness-for-discharge occurs at the same time as the 1hr assessment, the 1hr assessment (the last obtained score) will be carried forward to 2hr and to the discharge assessment.
- vi) For a patient without rescue drug, if readiness-for-discharge occurs at the same time as the 2hr assessment, the 2hr assessment will be carried forward to the readiness-for-discharge assessment.

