6.4.5 Concomitant Medications/Rescue Drugs

To ensure optimal patient management, additional medications, e.g. epinephrine, steroids, or etc., may be given during the study if deemed necessary by the investigator/designee. However, if without medical complication, all effort should be made to have the patient complete at least the 1 hour assessments prior to administration of the rescue medication. If rescue medication is needed very shortly after study drug administration (e.g. within ~10 -15min), this indicates that the patient might have anaphylaxis. This patient should be withdrawn from the study, because he/she should have been excluded during screening.

The product label of the rescue drugs should be followed to determine the appropriate dose.

The identity, dose, frequency and route of administration of all medications being taken prior to study enrolment will be recorded, as well as all concomitant medications administered during the study (rescue drug).

6.5 *Clinical and Safety Evaluations*

Study procedures and their timing are summarized in the Study Schedule, Protocol [Attachment A](#). All subjects who received at least one dose of study medication will be included in all analyses and safety analyses.

7. Clinical/Efficacy Outcome and Measures

7.1 *Primary Clinical Efficacy Measure*

The primary clinical efficacy outcome measure is the 2-hour patient rated Pruritus Severity Score Reduction/Change from Baseline (**D2**) as defined under [Attachment B](#), comparing between the two treatment groups.

7.2 *Key Secondary Clinical/Efficacy Measures*

The following key secondary clinical or efficacy measures will be assessed for each patient:

- 1) The need to return to treatment center after study discharge (i.e. 2nd visit within approximately ~24 hours after discharge)
- 2) Time spent at the treating center (time from treatment administration to Readiness for discharge)

7.3 *Other Clinical/Efficacy Measures*

The following other clinical or efficacy measures will be assessed for each patient:

- 1) Pruritus treatment success (% of patients), defined as a patient who had the Pruritus Severity Score Reduction of at least 1 unit for the 2-hour patient rated Pruritus Severity score from Baseline (**D2**) as defined under [Attachment B](#), comparing between the two treatment groups.
- 2) Patient rated pruritus severity scores reduction/change from baseline (D1 & D3) at 1 hour and at "time of discharge"

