**2. STUDY OBJECTIVES AND ENDPOINTS**

This will be a multicenter, parallel group, randomized, double-blind, active controlled, Phase III clinical study of cetirizine injection, 10 mg/mL, compared to diphenhydramine injection, 50 mg/mL (Benadryl or generic equivalent), in approximately 254 subjects with acute urticaria requiring treatment in Emergency Departments (ED), hospitals, Urgent Care Centers, or Allergy Clinics.

The objectives of this study are:

The primary objective of this study is to establish the non-inferiority of Cetirizine injection with respect to Diphenhydramine injection in reducing patient reported pruritus severity score at 2 hours after treatment of acute urticaria. The secondary objectives are as follows:

1. Record the percentage of subjects who return to treatment center after discharge (i.e. 2nd visit within 24 hours after discharge)
2. Record and compare sedation scores between treatments
3. Record and compare time-to-discharge between treatments
4. Record and compare changes in patient reported pruritus severity score at 1 hr post treatment and at time of discharge.
5. Record and compare extent of urticaria/erythema scores, and their changes from baseline at various time points after treatment.
6. Document the percentage of subjects experiencing adverse events (AEs) or serious adverse events (SAEs) from the both study drugs.
7. Document the percentage of subjects requiring rescue medication prior to discharge, e.g. epinephrine, bronchodilators, steroids, etc.,
8. Record symptom recurrence rate and additional symptoms occurrence within 24-48 hours after subject discharge from treatment centers.
9. Record the need for medication after discharge.

The primary demonstration of efficacy will be non-inferiority of cetirizine to diphenhydramine with regards to the change from baseline in patient rated pruritus severity at 2 hours post-treatment.

The following outcomes that will provide key support to the primary efficacy claim:

- 
- *Return to Treatment Center:* During the 24 and 48 hr follow up questions, subjects will be asked if they had to return to a treatment facility for their urticaria. Subjects will be flagged as either YES or NO.

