**10.2. Protocol Deviations**

All randomized subjects will be included in the ITT and SAF populations. If a violation hinders the ability to assess an efficacy outcome, the following approaches can be taken:

Examples:

- i) If patient does not have the disease intended to treat, the outcome for the 2 hr assessment will be set to the baseline values and the subjects will be considered a treatment failure. In this example, the “readiness for discharge” time will be missing, since the discharge time is confounded by the wrong disease.
- ii) if a subject receives an antihistamine within 2 hrs prior to baseline (not meeting exclusion #4), that subject will be considered a failure with change from baseline to 2 hr pruritus score and with change from baseline to 2 hr extent of urticaria score set to zero (0). In this example, sedation score will be missing since sedation is confounded by the antihistamine prior to baseline.

---

Inclusion of subjects in other efficacy endpoints will be dependent on availability of data for each assessment times point. Subject data will be reviewed for major protocol violations by a qualified clinical reviewer prior to database lock and unblinding. Subjects with any major protocol violations will be identified and excluded from the Per Protocol Population. A summary list of the individual subjects excluded, will be provided, sorted by treatment group with description of their protocol violation/deviation.

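### The rescue carry-forward rule in SAP 9.1 overwrites observed sedation scores: early rescue forces zero change, and later rescue freezes the last score

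*SAP*

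**What the plan says.** Comparing sedation is a stated secondary objective in SAP section 2: "Record and compare sedation scores between treatments". The score is taken at baseline, 1 hr, 2 hr and discharge. SAP 11.3 item 3 summarises the change at each time by arm, with descriptive statistics.

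SAP 9.1 has two carry-forward rules.

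- **Early discharge:** "assessments of pruritus, extent of urticaria, and sedation for subjects discharged prior to the 2 hr assessment will be carried forward". This fills slots where no score exists, and it is not the subject of this point.
- **Rescue:** "the pre-rescue score will be carried forward to all subsequent assessment including the 1hr, 2hr, and readiness-for-discharge-assessment". Sedation is covered because the rationale names it: "Any assessment of pruritus, extent of urticaria and sedation after administering rescue medication will be confounded with the response to rescue medication".

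The worked examples show that the rescue rule replaces recorded data. With rescue at 30 minutes, baseline goes into the later slots "regardless of the existing assessments at 1hr and 1.5hr (the discharge assessment". With rescue at 3 hr (example iii), the 1 hr and 2 hr scores stand and "the 2hr scores (the last pre-rescue-scores) will be carried forward to the discharge assessment".

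On timing, Protocol 6.4.5 asks that, if there is no medical complication, "all effort should be made to have the patient complete at least the 1 hour assessments prior to administration of the rescue medication". Neither document provides a sedation table based on observed scores, as a main or a sensitivity analysis.

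**The concern.** Carrying the pre-rescue score forward keeps relief due to rescue from being credited to the study drug. For pruritus that is conservative: a patient rescued early counts as not improved. Sedation is an unwanted effect, so the same step works the other way. A patient rescued at 30 minutes has already received the single study injection, and any sedation recorded at 1 hr is then replaced by a value taken before dosing. The table shows no change.

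When rescue comes later, the rule holds sedation at its last pre-rescue level even if the patient was observed to recover. That can leave a non-zero analysed score at discharge, although Protocol section 4 lists a sedation score of 0 among the criteria for readiness for discharge.

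At stake is whether the table for secondary objective 2 describes the sedation that patients reported.

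**Working it through.** The plan gives no figure to reproduce here. The check applies the 9.1 rule to example patients and then scales the result.

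**Step 1. The rule applied to single patients.** The last score before first rescue replaces all later scores. The score values are illustrative, because the scale in Protocol Attachment B is redacted.

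| First rescue | Discharge | Observed: baseline; 1 hr, 2 hr, discharge | Analysed: 1 hr, 2 hr, discharge |
|---|---|---|---|
| 0.5 hr | 2.5 hr | 0; 2, 1, 0 | 0, 0, 0 |
| 0.5 hr | 2.5 hr | 1; 2, 2, 1 | 1, 1, 1 |
| 1.25 hr | 2.5 hr | 0; 2, 1, 0 | 2, 2, 2 |
| 1.25 hr | 3 hr | 0; 0, 2, 1 | 0, 0, 0 |
| 3 hr | 4 hr | 0; 2, 1, 0 | 2, 1, 1 |

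Rows 1 and 2 give zero change, and in row 2 the score itself is not zero. Row 3 keeps the 1 hr score and overstates 2 hr and discharge. Row 4 loses sedation that rose after rescue. Row 5 overstates discharge only.

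**Step 2. Share of an arm forced to zero change at 1 hr.** Let r be the rescue rate and q the share of rescues given before 1 hr. The share is r × q. Both inputs are assumptions; 127 per arm is from SAP 9.11.

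- Low: 0.05 × 0.10 = 0.005, and 127 × 0.005 = 0.6 patients.
- Middle: 0.10 × 0.50 = 0.05, and 127 × 0.05 = 6.4 patients.
- High: 0.20 × 1.00 = 0.20, and 127 × 0.20 = 25.4 patients.

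**Step 3. Effect on the between-arm difference at 1 hr.** Assume true mean changes of 0.5 (arm A) and 1.0 (arm B), with rescued patients similar to the rest of their arm. Analysed difference = 1.0 × (1 − r_B q) − 0.5 × (1 − r_A q). The true difference is 0.50.

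| r_A | r_B | q | Analysed difference |
|---|---|---|---|
| 5% | 5% | 25% | 0.9875 − 0.49375 = 0.494 |
| 10% | 10% | 50% | 0.95 − 0.475 = 0.475 |
| 20% | 20% | 100% | 0.80 − 0.40 = 0.40 |
| 5% | 15% | 50% | 0.925 − 0.4875 = 0.438 |
| 15% | 5% | 50% | 0.975 − 0.4625 = 0.512 |

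Equal early rescue shrinks the difference. Unequal rescue can shrink or enlarge it.

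**Step 4. The opposite direction within an arm.** Suppose 5% of an arm follow row 3 of step 1. Their analysed scores exceed the observed ones by 2 − 1 = 1 at 2 hr and by 2 − 0 = 2 at discharge. The arm mean rises by 0.05 × 1 = 0.05 at 2 hr and 0.05 × 2 = 0.10 at discharge.

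**The case against.** **Rescue may itself sedate.** The rescue lists in the protocol are open-ended, and SAP section 2 defines rescue as any other medication for urticaria symptoms. A sedating rescue drug is therefore possible, and the confounding rationale is coherent. This stands, but it supports identifying those patients rather than substituting a baseline score that carries no information about the study drug.

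**Early rescue should be uncommon.** Protocol 6.4.5 asks for the 1 hr assessment first where possible and withdraws patients who need rescue within about 10 to 15 minutes. This stands and limits how often change is forced to zero. It does not prevent the freezing after later rescue.

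**Sedation is not a key endpoint.** Protocol 10.2.8 plans no inferential comparison for it, and SAP 9.3 allows nominal p-values at most. This stands.

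**Sedation can also be reported as an adverse event.** SAP 9.1 does not touch that route. This stands in part, because event counts do not replace the planned comparison of scores.

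**A score of 1 or more near discharge is foreseen.** Note i under the discharge criteria in Protocol section 4 covers patients who are otherwise fit to leave. A non-zero analysed discharge score is therefore not impossible in itself. The fault is that it can displace an observed 0.

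**SAP 10.2 might look like a contradiction.** In its example ii, "sedation score will be missing since sedation is confounded by the antihistamine prior to baseline". A reader might infer that the SAP treats the same problem in two ways. The documents do not support that. There the antihistamine precedes baseline, so no clean score exists, whereas under 9.1 a clean pre-rescue score does.

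**Conclusion.** The point holds as a limited one. SAP 9.1 replaces observed sedation scores after rescue. Rescue before 1 hr gives zero change. Later rescue freezes the last score, which may overstate sedation or hide a later rise.

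A reader might go further and infer that sedation is understated in every rescued patient. The documents do not support that: example iii keeps the 1 hr and 2 hr scores, and step 4 shows overstatement. Nor do they present sedation as the test drug's main advantage. Protocol section 2 lists it beside duration of action, anticholinergic effects, earlier discharge and symptom recurrence.

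The between-arm bias has no fixed sign. Over the assumed inputs, a true 1 hr difference of 0.50 is analysed as 0.40 to 0.51. The actual size is unknown, because rescue rates and timing by arm are not given. SAP 9.9 is redacted, so the sedation derivations cannot be seen in full, but 9.1 itself names sedation. The primary and key secondary tests are unaffected.

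**What to change.** In SAP 9.1, remove sedation from the rescue carry-forward rule. Summarise sedation as observed by arm at each assessment. Flag rescued patients, and mark separately those whose rescue drug is sedating. Keep the carried-forward version as a supplementary table.

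Because 9.1 lets rescue override early discharge, add that a rescued patient who leaves before 2 hr falls under the early-discharge rule for sedation, using the last observed score. Make the change before unblinding.

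The cost is a short wording change and one extra table. The scores are already collected, and conduct, sample size and the primary analysis do not change. The downside is that observed scores after a sedating rescue drug include that drug's effect. The flag and the supplementary table make this visible.

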Just before the study medication is administered, the study investigator or designee will record the following baseline data: vital signs, the extent of urticaria and erythema, the severity of pruritus by patient, and the level of sedation by patient. See [Attachment B](#) for detailed description of symptom assessment. The same measures will be assessed again at 1 hour and/or 2 hours after the injection, and/or at the Time of "Readiness for Discharge" which can happen at any time after the 1-hour assessment if the symptom score has reached zero at 1hr. If symptom score is not zero prior to 2 hr, patient must be kept at the treatment center for at least 2 hours. At these same time intervals, participating patients will be asked to self-rate (recorded by study staff) the severity of their pruritus and their level of sedation. The patient's responses will be recorded by the investigator/designee on the designated Source Document or eCRF as "patient assessment scores". The time that the investigator/designee determines that patient is physically and mentally fit to be discharged from the center (Time of "Readiness for Discharge"), , will be recorded in the source documents. If the Time of "readiness for discharge" happens longer than 20 minutes from the previous assessment, then the "readiness for discharge assessment" should be done. If the Time of "readiness for discharge" happens within 20 minutes of the previous assessment and the symptom score does not change from the previous assessment, then the "readiness for discharge" assessment is not needed, because the previous assessment can be treated as the "readiness for discharge assessment".

Site staff should ensure that the patient has appropriate transportation to their destination; under no circumstances should a study participant be permitted to drive themselves if the sedation score is at "1" or higher. The time that the patient actually leaves the treatment center is also recorded.

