**9.11. Changes from Protocol Planned Analysis**

The protocol included collecting information on the reason for use of rescue drugs (secondary objective #7), however, it was determined at the time of CRF development that capturing such data would not add to the determination that a rescue medication was given. Therefore, this was not captured.

The sample size justification in the protocol was not updated to match the final methodology used. While both the protocol and the SAP sample size justifications results in the need for 127 subjects per treatment arm, the assumptions in this SAP are more indicative of the actual assumptions and methodology used to arrive at this sample size.

The protocol did not make provisions for subjects who needed to be hospitalized or kept in the ED overnight for observations. The SAP covers the needs to treat the time spent at the treatment center to “missing” for these subjects.

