## 11. EFFICACY ANALYSES

### 11.1. Primary Endpoint

The primary clinical outcome measure is patient rated severity of pruritus at 2 hr post-treatment. The primary analysis will test for the non-inferiority of cetirizine to the active comparator, diphenhydramine, for the mean change from baseline in patient rated pruritus at 2 hours. See [Section 9.9](#) for derivation of this endpoint. Using the notation of [Gupta, 2011](#), the NI margin of -0.50 will be used to test the hypothesis:

$$H_0: \text{CCI} \quad \text{CCI}$$

---

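### No score is visibly required at rescue, so a patient who relapses and is rescued between 1 h and 2 h enters D2 with a 1 h score up to about an hour old

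*SAP*

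**What the plan says.** **When scores are taken.** Protocol section 4 records pruritus, extent of urticaria and sedation just before dosing, and then: "The same measures will be assessed again at 1 hour and/or 2 hours after the injection", and/or at readiness for discharge. Protocol Attachment A and SAP Table 1 list the same times. Neither has an entry triggered by rescue.

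**What happens at rescue.** Protocol 6.4.5 leaves rescue to the investigator but adds that, absent medical complication, "all effort should be made to have the patient complete at least the 1 hour assessments prior to administration of the rescue medication". It does not ask for a score when rescue is decided.

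**How D2 is then set.** For rescue before the 2 h assessment, SAP 9.1 states that "the last pre-rescue assessments will be carried forward to the 2 hr assessment and to any post-rescue assessments". Scores obtained after rescue are set aside. In examples i and ii, rescue at 30 minutes carries the baseline score, so D2 = 0. By the same rule, rescue between 1 h and 2 h carries the 1 h score.

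**How rescued patients are regarded.** Protocol section 4, in its discharge criteria, counts a rescued patient as effectively treated by the rescue drug and not by the study drug.

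**The concern.** Take a patient whose itch falls from 3 to 1 at 1 h, returns to 3, and is rescued at 1 h 50 min. (The scores are illustrative, because the pruritus scale is redacted.) D2 records a 2-unit reduction, although at the time of rescue there was none. The patient would also count as a pruritus treatment success under SAP section 2, while Protocol section 4 says the study drug did not treat the patient effectively.

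Patients who do well are handled differently. Protocol section 4 requires a fresh assessment when readiness for discharge comes more than 20 minutes after the previous one, and SAP 9.1 example iv carries that fresh score to 2 h.

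The missing information cannot be recovered later. SAP 9.11 says that the reason for rescue was not captured, so without a score at rescue nobody can tell whether itch had worsened. In a non-inferiority trial, unrecorded relapse that is more common on cetirizine would make a worse arm look closer to the comparator.

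**Working it through.** **Inputs from the documents**
- Margin: SAP 11.1 states that "the NI margin of -0.50 will be used to test the hypothesis". With a negative margin and a null hypothesis of the form less than or equal to it, I read D2 as a reduction (larger is better) and the difference as cetirizine minus diphenhydramine.
- Sample size: SAP 9.11 says the justification "results in the need for 127 subjects per treatment arm".
- Power: in SAP section 6, the sample size "is needed to provide 90% statistical power to determine that Cetirizine will be non-inferior to diphenhydramine".
- Alpha: SAP section 6 gives it as "using 1-sided test at alpha CCI", so the level is redacted. SAP section 9 says: "The assumed overall type I error rate/significance level for the primary efficacy outcome is 5%, two-sided, unless otherwise specified". I use one-sided 0.025, with 0.05 as a variant.
- Not available: the SD (redacted), rescue rates by arm, timing of rescue, and worsening before rescue.

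**Step 1: the plan's own figure.** The 127 per arm cannot be reproduced without the SD and alpha, but it can be inverted for a true difference of zero:

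SD = 0.50 × √(127/2) / (z₁₋α + z₀.₉₀)
- α = 0.025: 0.50 × 7.969 / 3.242 = 1.229
- α = 0.05: 0.50 × 7.969 / 2.926 = 1.362

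If the 127 includes 10% dropout, the SD at 0.025 is 1.166. These are implied values, not the plan's stated SD.

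**Step 2: what D2 contains, by time of rescue (no score at rescue)**

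| First rescue | Score carried | D2 | Too favourable if |
|---|---|---|---|
| Before the 1 h score | Baseline | 0 | itch rose above baseline |
| After the 1 h score, before 2 h | 1 h, up to about 60 min old | baseline minus 1 h score | itch worsened after 1 h |
| After the 2 h score | None needed for D2 | as observed | not affected |

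**Step 3: bias in the difference.** Let r be the proportion of an arm rescued between the 1 h and 2 h scores, and w the mean unrecorded worsening in those patients.

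Bias = w_cet × r_cet − w_diph × r_diph, which is w × (r_cet − r_diph) when w is equal in both arms.

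Assumed: a gap of 3 to 6 points (0.03 × 127 = 3.8 patients; 0.06 × 127 = 7.6) and w of 1 to 2 units.
- Low: 0.03 × 1 = 0.03; 0.03/0.50 = 6% of the margin
- High: 0.06 × 2 = 0.12; 0.12/0.50 = 24%
- If only half of the excess rescues are late relapses: 0.015 to 0.06, or 3% to 12%
- Equal rates and equal w, or w = 0: no bias

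**Step 4: effect on the test.** At a true difference of −0.50, with n = 127 per arm:

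Type I error = Φ(bias/SE − 1.96), SE = SD × √(2/127)

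| Bias | For example | SD 1.229 (SE 0.154) | SD 1.0 (SE 0.125) |
|---|---|---|---|
| 0 | equal rates and w | 2.5% | 2.5% |
| 0.05 | 5 points × 1 unit | 5.1% | 5.9% |
| 0.10 | 5 points × 2 units | 9.5% | 12.2% |

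**Step 5: the extreme.** To use up the whole margin, late-rescue rates would have to differ by 0.50/1 = 50 points at w = 1, or 0.50/2 = 25 points at w = 2.

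**The case against.** A reader might infer that the carried score can never reflect the state that prompted rescue, and that the rule always flatters the arm with more rescue. The documents support neither.

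- Protocol 6.4.5 steers staff toward completing the 1 h score before rescue. A patient scored at 1 h and rescued straight afterwards carries a current value. This stands, but leaves the rest of the 1 h to 2 h window uncovered.
- Rescue is at the investigator's discretion. It may follow itch that simply failed to improve, or symptoms other than itch. Then there is no hidden worsening, and if itch was still falling the carried score understates benefit. This stands, so the direction is conditional.
- Rescue before the 1 h score already counts as no improvement.
- A reader might extend the point to withdrawals. The carry-forward rule in SAP 9.1 covers early discharge and rescue only. Withdrawal falls under SAP 9.6, which uses available data and states no 2 h rule. That is a separate gap, and Protocol 5.3 asks sites to try to complete observations.
- Attachment B, SAP 9.9 and part of SAP 11.1 are redacted, and SAP 11.2 is not in the text available. A score at rescue or a sensitivity analysis may be specified there.
- Rescue use and investigator-judged effective treatment are tabulated by arm (SAP 11.3), so an imbalance would be seen. The per-protocol definition gives use of rescue as an example reason for exclusion, but excluding these patients drops failures instead of scoring them.

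**Conclusion.** The point holds for rescue between the 1 h and 2 h scores, as far as the visible text shows. D2 is too favourable for a patient whose itch worsened after the 1 h score. The treatment comparison is biased only if such relapses differ by arm in frequency or size, and then toward the arm with more of them. For rescue before the 1 h score the problem arises only if itch rose above baseline.

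The range of 0.03 to 0.12 (6% to 24% of the margin) rests wholly on assumed rescue gaps and worsening, and halves if half of the excess rescues are late relapses. A shift of that size would not consume the margin, but under the implied SD a bias of 0.05 to 0.10 would raise the one-sided error from 2.5% to between 5.1% and 9.5%. The documents do not show that such an imbalance is expected. This is an inexpensive improvement to data collection and analysis; it is not evidence that the primary result would be wrong.

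**What to change.** 1. **Protocol 6.4.5 and Attachment A:** add a timed patient pruritus and sedation score and a physician extent score immediately before the first rescue drug, whenever this does not delay care. When and how rescue is given is unchanged.
2. **SAP 9.1, rescue after the 1 h score:** use the score at rescue as the last pre-rescue assessment.
3. **SAP 9.1, rescue before the 1 h score:** keep the baseline carry-forward, and use the score at rescue only if it is worse than baseline. Without this limit, a patient going from 3 to 2 at 30 minutes and then rescued would change from D2 = 0 to a 1-unit benefit.
4. **Score not taken:** apply the present rule and report the number by arm.
5. **Sensitivity analysis:** set D2 to zero for every patient rescued before 2 h. A 5-point gap in rescue after the 1 h score, with a mean 1 h improvement of 1 unit in those patients, would move the difference by 0.05 × 1 = 0.05. Also report how many patients had a carried score already worse than baseline, because zero is lenient for them.

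**Cost.** One more eCRF line and a few SAP sentences. SAP 9.11 speaks of CRF development as past, so item 1 may be too late; item 5 needs no new data and can be done regardless. The score will be missing in urgent cases, and mean D2 may be slightly less favourable.
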